## 17. Index of Figures

Header	Figure Number	Name	Analysis Set
14.		Tables, Figures, and Graphs Referred to but not Included in the Text	
14.2		Efficacy Data Summary Figures and Tables	
14.2.1		Proportion of Subjects' Eyes who Show less than 0.5 D Myopia Progression (Normalized SER) from Baseline	
	14.2.1.1.2	Proportion of Subjects' Eyes who Show less than 0.5 D Myopia Progression (Normalized SER) from Baseline in Stage 1 by Treatment Group and Visit	Stage 1 Modified Intent-to-Treat Set
	14.2.1.2.3	Proportion of Subjects' Eyes who Show less than 0.5 D Myopia Progression (Normalized SER) from Baseline in Stage 1 by Treatment Group and Visit	Stage 1 Intent-to-Treat Set
	14.2.1.2.5	Proportion of Subjects' Eyes who Show less than 0.5 D Myopia Progression (Normalized SER) from Baseline in Stage 1 by Treatment Group and Visit	Stage 1 Modified Per Protocol Set
	14.2.1.2.7	Proportion of Subjects' Eyes who Show less than 0.5 D Myopia Progression (Normalized SER) from Baseline in Stage 1 by Treatment Group and Visit	Stage 1 Per Protocol Set
14.2.2.1		Change from Baseline in Normalized SER	
	14.2.2.1.2	Normalized SER (D) in Stage 1 by Treatment Group and Visit	Stage 1 Modified Intent-to-Treat Set
	14.2.2.1.3	Change from Baseline in Normalized SER (D) in Stage 1 by Treatment Group and Visit	Stage 1 Modified Intent-to-Treat Set
	14.2.2.1.5	Normalized SER (D) in Stage 1 by Treatment Group and Visit	Stage 1 Intent-to-Treat Set
	14.2.2.1.6	Change from Baseline in Normalized SER (D) in Stage 1 by Treatment Group and Visit	Stage 1 Intent-to-Treat Set
14.2.2.2		Change from Baseline in Axial Length	
	14.2.2.2.2	Axial Length (mm) in Stage 1 by Treatment Group and Visit	Stage 1 Modified Intent-to-Treat Set
	14.2.2.2.3	Change from Baseline in Axial Length (mm) in Stage 1 by Treatment Group and Visit	Stage 1 Modified Intent-to-Treat Set
	14.2.2.2.5	Axial Length (mm) in Stage 1 by Treatment Group and Visit	Stage 1 Intent-to-Treat Set
	14.2.2.2.6	Change from Baseline in Axial Length (mm) in Stage 1 by Treatment Group and Visit	Stage 1 Intent-to-Treat Set
14.2.3.1		Proportion of Subjects' Eyes who Show less than 0.75 D Myopia Progression (Normalized SER) from Baseline	

This document is confidential.

Header	Figure Number	Name	Analysis Set
	14.2.3.1.2	Proportion of Subjects' Eyes who Show less than 0.75 D Myopia Progression (Normalized SER) from Baseline in Stage 1 by Treatment Group and Visit	Stage 1 Modified Intent-to-Treat Set
	14.2.3.1.4	Proportion of Subjects' Eyes who Show less than 0.75 D Myopia Progression (Normalized SER) from Baseline in Stage 1 by Treatment Group and Visit	Stage 1 Intent-to-Treat Set
14.2.3.2		Change from Baseline in Normalized SER	
	14.2.3.2.2	Kaplan-Meier Curve for Time to Change from Baseline in Myopia Progression of -0.75 D Normalized SER in Stage 1 by Treatment Group	Stage 1 Modified Intent-to-Treat Set
	14.2.3.2.4	Kaplan-Meier Curve for Time to Change from Baseline in Myopia Progression of -0.75 D Normalized SER in Stage 1 by Treatment Group	Stage 1 Intent-to-Treat Set
14.2.4.1		Change from Baseline in Normalized SER in Stage 2	
	14.2.4.1.2.2	Normalized SER (D) in Stage 2 by Stage 1 to Stage 2 Treatment Description and Visit	Stage 2 Modified Intent-to-Treat Set
	14.2.4.1.2.3	Change from Stage 2 Baseline in Normalized SER (D) in Stage 2 by Stage 1 to Stage 2 Treatment Description and Visit	Stage 2 Modified Intent-to-Treat Set
	14.2.4.1.2.4.1	Normalized SER (D) in Stage 2 by Stage 1 to Stage 2 Treatment Description and Visit	Stage 2 Intent-to-Treat Set
	14.2.4.1.2.4.2	Change from Stage 2 Baseline in Normalized SER (D) in Stage 2 by Stage 1 to Stage 2 Treatment Description and Visit	Stage 2 Intent-to-Treat Set

This document is confidential.

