**Table 2: Visit Window Schedule (for analysis of PPS)**

Visit	Scheduled Visit Day	Visit Window (±28day except Month 36 visit, ±42 days for Month 36)
Baseline	Day 1	≤ Day 1
Month 6	Day 182	Day 154 - Day 210
Month 12	Day 365	Day 337 – Day 393
Month 18	Day 548	Day 520 – Day 576
Month 24	Day 731	Day 703 – Day 759
Month 30	Day 913	Day 885 – Day 941
Month 36	Day 1096	Day 1068 – Day 1124
Month 42	Day 1278	Day 1250 – Day 1306
Month 48	Day 1461	Day 1419 – Day 1503

In case 2 or more visits occur within a visit window, the closest visit to the scheduled visit will be used for summaries and analysis. If 2 visits are equidistant from the scheduled visit, then the later visit will be used.

Stage 1 is scheduled to run from Baseline until the Month 36 visit. Stage 1 will end when the subject leaves the study or completes their Month 36 visit, whichever is earlier. Stage 2 will begin on the day of first dose after re-randomization.

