8.3.7. Between-treatment group (Atropine Sulfate Ophthalmic Solution, 0.02% versus Vehicle)  
Difference in the Time to Change from Baseline in Myopia Progression of -0.75 D SER

A tertiary analysis will be performed on the between-treatment group (Atropine Sulfate Ophthalmic Solution, 0.02% versus vehicle) difference in the time to change from baseline in myopia progression of -0.75 D SER.

The time to change in myopia progression of -0.75 D SER (days) = (first date with a change in myopia progression of -0.75 D or more – first date of treatment) +1. For subjects that were not observed to have a change in myopia progression of -0.75 D or more = Time to change in myopia progression of -0.75 D SER (days) [censored] = (Date of last known visit of Stage 1 – (first date of treatment) + 1.

The point estimate of the hazard ratios and the associated 95% confidence intervals will be obtained using the Cox proportional hazards regression model with fixed effects for treatment group, age at baseline, and baseline SER as covariates. An approximate Chi-square test based on Wald statistic will be used to compare treatment groups.

Summary statistics and associated survival curves (Kaplan-Meier estimates) will be presented along with a full data listing by treatment group.

Summary statistics will be presented along with a full data listing by treatment group.

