	14.2.4.4.1	Summary of Time to Change from Stage 2 Baseline in Myopia of -0.75 D Normalized SER in Stage 2 by Stage 1 to Stage 2 Treatment Description	Stage 2 Modified Intent-to-Treat Set
	14.2.4.4.2	Summary of Time to Change from Stage 2 Baseline in Myopia of -0.75 D Normalized SER in Stage 2 by Stage 1 to Stage 2 Treatment Description	Stage 2 Intent-to-Treat Set
14.2.4.5		New Prescriptions Given during Stage 2	
	14.2.4.5.1	Summary of the New Prescriptions Given during Stage 2	Stage 2 Modified Intent-to-Treat Set
	14.2.4.5.2	Summary of the New Prescriptions Given during Stage 2	Stage 2 Intent-to-Treat Set
14.2.4.6		Proportion of Subjects who Progressed to High Myopia (Normalized SER -6.00 D or more myopic) at Month 48 by Baseline Myopia in Stage 2	
	14.2.4.6.1	Summary of the Proportion of Subjects who Progressed to High Myopia (Normalized SER -6.00 D or more myopic) at Month 48 by Baseline Myopia in Stage 2	Stage 2 Modified Intent-to-Treat Set

This document is confidential.

Header	Table Number	Name	Analysis Set
	14.2.4.6.2	Summary of the Proportion of Subjects who Progressed to High Myopia (Normalized SER -6.00 D or more myopic) at Month 48 by Baseline Myopia in Stage 2	Stage 2 Intent-to-Treat Set
14.2.4.7		Interaction between Demographic Variables and Normalized SER in Stage 2	
	14.2.4.7.1.1	Summary of the Change from Stage 2 Baseline in Normalized SER (D) in Stage 2 by Stage 1 to Stage 2 Treatment Description and Visit (6-8 years old vs. 9-10 years old)	Stage 2 Modified Intent-to-Treat Set
	14.2.4.7.1.2	Summary of the Change from Stage 2 Baseline in Normalized SER (D) in Stage 2 by Stage 1 to Stage 2 Treatment Description and Visit (6-8 years old vs. 9-10 years old)	Stage 2 Intent-to-Treat Set
	14.2.4.7.2.1	Summary of the Change from Stage 2 Baseline in Normalized SER (D) in Stage 2 by Stage 1 to Stage 2 Treatment Description and Visit (Baseline SER -0.50 to -3.00 D vs. -3.01 to -6.00 D D)	Stage 2 Modified Intent-to-Treat Set
	14.2.4.7.2.2	Summary of the Change from Stage 2 Baseline in Normalized SER (D) in Stage 2 by Stage 1 to Stage 2 Treatment Description and Visit (Baseline SER -0.50 to -3.00 D vs. -3.01 to -6.00 D D)	Stage 2 Intent-to-Treat Set
	14.2.4.7.3.1	Summary of the Change from Stage 2 Baseline in Normalized SER (D) in Stage 2 by Stage 1 to Stage 2 Treatment Description and Visit (Asian vs. Non-Asian)	Stage 2 Modified Intent-to-Treat Set

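### The tail of the Kaplan-Meier curves for time to -0.75 D progression overstates progression, because completers enter or leave on their own Month 36 exam dates

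*SAP*

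**What the plan says.** SAP 8.3.7 defines the tertiary endpoint for 0.02% against Vehicle, and 8.3.8 applies the same method to 0.01%.

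- **Event time:** days from first treatment to the "first date with a change in myopia progression of -0.75 D or more".
- **Censoring time** for a child without the event: days from first treatment to the "Date of last known visit of Stage 1".
- **End of Stage 1** (SAP 6.4): "Stage 1 will end when the subject leaves the study or completes their Month 36 visit, whichever is earlier". A completer without progression is therefore censored on the day of the Month 36 exam. A drop-out is censored at an earlier last visit.
- **Display:** "Summary statistics and associated survival curves (Kaplan-Meier estimates) will be presented along with a full data listing by treatment group". SAP 17 lists the curves as Figures 14.2.3.2.2 (mITT) and 14.2.3.2.4 (ITT), each under the title "Kaplan-Meier Curve for Time to Change from Baseline in Myopia Progression of -0.75 D Normalized SER in Stage 1 by Treatment Group".
- **Treatment comparison:** a "Cox proportional hazards regression model with fixed effects for treatment group, age at baseline, and baseline SER as covariates", with a Wald test.

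The visit windows in SAP 6.4 assign exams to visits but do not replace the dates in the 8.3.7 formula. Section 8.3.7 names no scheduled-time or interval-censored estimator and no day on which the curve is to be read.

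**The concern.** Refraction is measured six times in Stage 1, at Months 6 to 36. At Months 6 to 30 a child found unprogressed who continues stays in the risk set, so the spread of exam dates does little harm. At Month 36 each remaining child is examined once, on a personal date, and leaves the risk set that day as an event or as censored. Kaplan-Meier cannot tell that a child censored on day 1085 has already had the Month 36 exam and passed it. It treats that child as lost, and an event found on day 1105 is divided by the few children not yet seen.

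The end of each curve then depends partly on appointment order and tends to fall below the true event-free share. A reader who takes the three-year result from the end of the figure would see too much progression in every arm. The value could also look inconsistent with the Month 36 proportions below 0.75 D reported under SAP 8.3.5 and 8.3.6.

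**Working it through.** **Plan figures used.** Neither document gives a -0.75 D rate or a Kaplan-Meier value, so there is no stated result to reproduce. The planning inputs can be checked. Exact enumeration of Fisher's test at 0.25 against 0.07 gives 95.6% power for 136 and 91, and 90.1% for 91 and 91 (stated: 95% and 90%). Inflating for 27% drop-out gives 91/0.73 = 124.7, rounded up to 125, and 136/0.73 = 186.3 (planned: 125 and 186).

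**Closed form for the last visit.** Let n children be examined on different days in the Month 36 window, each with probability p of a new event. The correct factor is 1 - p. The expected Kaplan-Meier factor is the product of (1 - p/m) for m = 1 to n.

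| n | p | Correct | Kaplan-Meier on exam dates |
|---|---|---|---|
| 50 | 0.17 | 0.83 | 0.454 |
| 13 | 0.28 | 0.72 | 0.382 |
| 20 | 0.10 | 0.90 | 0.692 |

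**Applied to the planning rates.** Assume, for illustration only, that the 0.5 D responder rates (0.07 and 0.25) also hold at 0.75 D, with a constant hazard per visit.

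- Vehicle: hazard 1 - 0.07^(1/6) = 0.358. Event-free after Month 30: 0.07^(5/6) = 0.109. Examined at Month 36: 125 × 0.73 × 0.109 ≈ 10. Factor 0.310, so the end value is 0.109 × 0.310 = 0.034.
- 0.02%: hazard 1 - 0.25^(1/6) = 0.206. Event-free after Month 30: 0.315. Examined: 186 × 0.73 × 0.315 ≈ 43. Factor 0.392, so the end value is 0.315 × 0.392 = 0.124.

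The closed form assumes that no two children share an exam day. Ties soften the effect, so the next step is simulation.

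**Simulation** (125 and 186 children, 27% drop-out, whole-day visit scatter, 1,000 trials per case). With visits within 14 days:

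| | Vehicle | 0.02% | Gap |
|---|---|---|---|
| Scheduled visit days | 0.070 | 0.250 | 0.181 |
| End of curve, exam dates | 0.033 | 0.136 | 0.103 |

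The gap loss is 1 - 0.103/0.181 = 43%. Without drop-out it is 42%, so drop-out is not the cause. Single trials vary widely: median loss 39%, interquartile range 17% to 67%.

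**Sensitivity of the gap loss at the end of the curve.**

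- Scatter of 42 days: 49%. Scatter of 91 days, the half-width of the Month 36 window in SAP Table 1: 51%.
- Other shapes of progression over time, same rates: 43% and 65%.
- A -0.75 D rate derived from the 0.5 D planning rates (normal progression, assumed SD 0.6 to 1.2 D, measurement noise 0 to 0.25 D): 28% to 46%.
- Assumed event-free shares of 0.15/0.35: 32%; 0.20/0.40: 27%; 0.30/0.50: 12%; 0.40/0.60: none; 0.50/0.70: the gap is 13% wider.

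The end value stays too low in both arms even where the gap does not shrink; at 0.40/0.60 the curves end at 0.261 and 0.466.

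**Reading day.** In the base case the gap read at Day 1096 is about 3% larger than the true one, and one week before the window closes it is 7% smaller. Under the two other shapes, the gap at Day 1096 was 10% and 18% smaller.

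**Cox model.** The mean log hazard ratio is -0.666 on exam dates and on scheduled days.

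**The case against.** The strongest reply is that this is the last few days of a tertiary figure. Treatments are compared by the Cox hazard ratio, which does not move. The endpoint is outside the fixed sequence in SAP 8. No Kaplan-Meier landmark estimate is specified, SAP 13.2.5.4 puts study visits on the X-axis, and the Month 36 share below 0.75 D is reported separately. All of this stands and limits the weight of the point. It does not remove it: the axis rule governs display and leaves the day-based time variable unchanged, and the final plotted value is still biased.

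Four stronger readings are tempting but not supported:

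- **That the gap shrinks by 40% as a fact.** The 0.07 and 0.25 are 0.5 D responder rates. At other plausible -0.75 D rates the loss is small or absent.
- **That the whole curve is wrong.** The distortion is in the tail. In the base case Day 1096 shows no loss of separation.
- **That the atropine benefit is understated on every scale.** This concerns the absolute gap. The ratio of event-free shares rises, from 0.25/0.07 = 3.6 to 0.136/0.033 = 4.1.
- **That Stage 2 is distorted as well.** SAP 16 promises only a "Summary of Time to Change from Stage 2 Baseline in Myopia of -0.75 D Normalized SER in Stage 2" and names no estimator, and SAP 17 lists no Stage 2 Kaplan-Meier figure. The point would apply there only if Kaplan-Meier estimates were produced.

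**Conclusion.** The point holds as a defect in how a tertiary result is displayed. As written, the tail of Figures 14.2.3.2.2 and 14.2.3.2.4 overstates progression in every arm; in the simulations the end value was too low in 97% to 100% of trials in each arm. Its effect on the separation between arms cannot be fixed from the documents. It is about 40% of the absolute gap if the planning rates are carried over to 0.75 D, roughly 28% to 46% if a -0.75 D rate is derived from them, and little or nothing if many more children stay unprogressed. These figures assume independent visit scatter and the planned sample sizes and drop-out. The hazard ratio, its test, and the primary and secondary analyses are not affected.

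**What to change.** In SAP 8.3.7 and 8.3.8, for the Kaplan-Meier estimates only:

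- Set both event and censoring times to the scheduled day of the visit (Months 6, 12, 18, 24, 30, 36).
- Always assign the Stage 1 Month 36 visit to Month 36. SAP Table 1 would otherwise place an exam after Day 1187 in Month 42.
- Count events before censorings at ties.

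An interval-censored (Turnbull) estimate is an acceptable alternative. The standard actuarial life table is not: it removes half of the censored children from the denominator. For n = 50 and p = 0.17 it gives 1 - 8.5/(50 - 41.5/2) = 0.71 where 0.83 is correct.

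The Cox analysis can stay as it is. Apply the same rule to Tables 14.2.4.4.1 and 14.2.4.4.2 only if Kaplan-Meier estimates are produced for Stage 2.

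The cost is one sentence and one derived time variable. The curve becomes a six-step curve. No new data are needed and no confirmatory test changes.

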## 18. Index of Listings

Header	Table Number	Name	Analysis Set (Example)
16.2		Subject Data Listings	
16.2.1		Discontinued Subjects	
	16.2.1.1	Subject Disposition	Enrolled Set
16.2.2		Protocol Deviations	
	16.2.2.1	Protocol Deviations	Enrolled Set
16.2.3		Subjects Excluded from the Efficacy Analysis	
	16.2.3.1	Inclusion/Exclusion Criteria	Enrolled Set
	16.2.3.2	Exclusions from Analysis Sets	Enrolled Set
16.2.4		Demographic Data	
	16.2.4.1	Demographics	Intent-to-Treat Set
	16.2.4.2	Medical History	Intent-to-Treat Set
	16.2.4.3	Ocular History	Intent-to-Treat Set
	16.2.4.4	Baseline Disease Characteristics	Intent-to-Treat Set
	16.2.4.5	Prior and Concomitant Medications	Intent-to-Treat Set
16.2.5		Compliance	
	16.2.5.1	Study Drug Adherence	Safety Set
	16.2.5.2	Study Drug Exposure and Treatment Compliance	Safety Set
16.2.6		Individual Efficacy Response Data	
	16.2.6.1	Cycloplegic Autorefraction	Intent-to-Treat Set
	16.2.6.2	Axial Length and Crystalline Lens Thickness	Intent-to-Treat Set
		Adverse Event Listings	
	16.2.7.1	Adverse Events	Safety Set
	16.2.7.2	Severe Adverse Events	Safety Set
	16.2.7.3	Study Drug Related Adverse Events	Safety Set
	16.2.7.4	Study Drug Related Serious Adverse Events	Safety Set
16.2.8		Listing of physical examination by subject	
	16.2.8.1.1	Urine Pregnancy Test	Intent-to-Treat Set
		Other Safety Data	
	16.2.8.2.1	Best Corrected Visual Acuity	Intent-to-Treat Set
	16.2.8.2.2	Photonic Pupil Size Measurement	Intent-to-Treat Set
	16.2.8.2.3	Slit lamp Examination	Intent-to-Treat Set
	16.2.8.2.4	Dilated Fundus Examination	Intent-to-Treat Set
	16.2.8.2.5	Tonometry	Intent-to-Treat Set
	16.2.8.2.6	Modified ATI Questionnaires	Intent-to-Treat Set
	16.2.8.2.7	Telephone Contact	Intent-to-Treat Set
	16.2.8.2.8	Vital Signs and Physical Findings	Intent-to-Treat Set

This document is confidential.
